6.2.1 Exercise intervention

During the initial assessment patients will be taught how to perform the exercises to complete at home during the intervention period. The exercise intervention is supervised by skilled physiotherapists and delivered via Infinity Connect app and a webcam⁷² at Rigshospitalet to a group of approximately 4–8 patients who exercise at home and communicate via a tablet. Each session is 60 min, i.e., 40 min of exercise and 20 min of patient education, three times per week for the prehabilitation period. The exercises used in the program are identified and selected amongst exercises used in previous exercise intervention studies and involves larger muscle groups with 50/50% exercises for upper and lower extremities, respectively.⁷³ The exercises are executed in four sets to achieve peripheral muscle fatigue and secondary dyspnea/breathlessness. Each set is carried out in a predefined period of 20 to 40 s with a maximum number of repetitions performed, i.e., 8 to 25 repetitions depending on the patients exercise capacity and motivation, but with the aim of 12 to 20 repetitions.^{73,74} In practice the training intensity is determined by using the self-rated Borg Scale, moderate intensity RPE 11-15, 50-60% VO₂peak.⁷⁴

The first week serve as a familiarization phase with the purpose to adapt to exercising, adjusting, and optimizing load and to avoid musculoskeletal overload injuries. Monitoring physical activity and providing motivation through phone calls weekly will be enhanced by incorporating a novel accelerometer system, offering activity level feedback (SENS innovation)⁷⁵ to guide healthcare staff. Participants in the intervention will be instructed to perform daily exercise tasks such as brisk walking and sit-stand exercises. Additionally, motivational phone calls will be made to participants in the intervention group, while healthcare staff will receive feedback on these patients, aiding to guide them in achieving their activity goals. Patients will also be asked to complete a diary describing physical activity outside the programmed session, included in a patient booklet. All study participants will wear the accelerometer from the screening phase until the day preceding the procedure, and again postoperatively until the day of discharge and for 30 days

thereafter.^{76,77} The technology platform provided to the patients includes a tablet and an accelerometer device to facilitate exercise training sessions and data collection.

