7.1 Primary outcome

Feasibility outcomes include:

Recruitment and retention rates. The recruitment rate will be determined by the number of individuals who participate in the study out of those who are eligible/admissible but refused to participate. First, we will evaluate the number of patients we are able to include in the study during the inclusion period. A proportion of 60% or more of patients awaiting elective CABG surgery who are eligible for the study is acceptable. Retention will be assessed by the percentage of participants who remain in the study from beginning to end of study (30 days post-surgery).

Attrition rates. Attrition is defined by the number of individuals who give consent to participate in the study but drop out before the end of the intervention period, regardless of group allocation.

Fidelity. Fidelity of delivery of the webcam-based exercise training intervention will be assessed qualitatively by 8-10 semi-structured interviews the day before surgery by a research nurse.

Adherence rates. Adherence to the interventions will be measured by using the number of telephone counselling and tele-exercise sessions delivered out of the theoretical number that could have been delivered based on the surgical wait time of each participant. Adherence to the homebased tele-exercise training sessions and telephone counselling by evaluating the number of sessions applied in the intervention group. This will be collected by patient recorded physical activity logbook, by weekly phone calls and completed by accelerometer data. Adherence with the prehabilitation program will be assessed against the target of individuals achieving > 70% of the prescribed exercise program (self-reported) + during the study follow-up with phone calls. Inclusion in the CABGpreHAB study must be attractive to at least 30% of eligible patients who meets the inclusion criteria. The interventions must be widely accepted, with at least 70% of included participants completing 70% or more of the planned sessions in the intervention group. This will be assessed by interviews addressing reasons for withdrawals from the study and at which stage of the study these occur.

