7.2 Secondary outcome

Secondary outcomes shown in **Table 1**. will assess the patients' responses to the multimodal prehabilitation programme and data will be collected on the following explorative outcomes shown in **Table 2**, measured at baseline, the day before surgery and 30 days after discharge.

Table 1. The patient related tests and outcome measures

Outcome variable	Measurement Instrument	What is the argument for this test or instrument?
TESTS		
Exercise capacity	6MWT	(6MWT) measures total walking distance completed in six minutes. ⁸⁸ Functional exercise capacity assessed as change from baseline by using the (6MWT) according to the American Thoracic Society guidelines. ⁸⁸
Muscle strength	30 seconds sit-to stand	Strength and endurance in leg assessed as change from baseline by 30 sec sit-to stand test. ⁸⁹
Muscle strength	Hand grip strength	The Hand grip strength measures the upper-body physical function assessed by hand grip strength using a hand-held dynamometer. ⁹⁰ Frailty assessed from baseline by Hand grip strength.
Body composition	BIA	Bio-electrical Impedance Analysis (BIA) estimates values for each body percentage, fat mass, fat-free mass, muscle mass and bone mass and total body water are assessed measuring bioelectrical impedance in the body using a Bioelectrical Impedance Analyzer. ⁹¹
Nutritional status	NRS 2002 + BMI, weight, height	Nutritional Risk Screening 2002 (NRS 2002) screening tool is a validated tool attributes scores of different levels of nutritional status to patients based on weight loss, BMI, and food intake, considering disease severity (degree of stress metabolism) and age. It is a toll recommended for detection of undernutrition and the risk of its development in hospital settings. Nutritional status assessed as changed from baseline. ⁷⁸ Body mass index BMI ⁹² at baseline,
Daily physical activity score	SENS® motion accelerometer	The SENS motion® system consist of a single-use miniature, waterproof tri-axial accelerometer, and a dedicated smart phone application. The accelerator will be placed on the lateral side of the patient's thigh at the assessment initial with a small waterproof Band-Aid. The participants will be asked to wear the SENS-accelerometer continuously for minimum four weeks during the intervention period and again post-surgery until end of follow up 30 days post index surgery. Physical activity assessed as changed from baseline by accelerator SENS innovation device. ⁷⁵
QUESTIONNAIRES		

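### No source named for the adherence outcome directly and objectively records attendance at the tele-exercise sessions, although staff are present at every one

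*Protocol*

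**What the plan says.** Section 7.1 of the protocol lists adherence among the primary feasibility outcomes and measures it as the "number of telephone counselling and tele-exercise sessions delivered out of the theoretical number that could have been delivered" during the individual wait for surgery. The next sentence speaks of sessions applied, and the acceptance criterion further down speaks of participants completing sessions.

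The sources are then fixed: "This will be collected by patient recorded physical activity logbook, by weekly phone calls and completed by accelerometer data". The exercise target is stated as "> 70% of the prescribed exercise program (self-reported) + during the study follow-up with phone calls".

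Three other places bear on these sources:

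- **Patient record.** Section 6.2.1 describes one patient-kept activity record: "Patients will also be asked to complete a diary describing physical activity outside the programmed session, included in a patient booklet".
- **Calls.** Section 6.2.1 gives the purpose of the exercise-related calls as "Monitoring physical activity and providing motivation through phone calls weekly". The end of section 6.2.5 plans one nurse counselling call and three physiotherapist-led web sessions per week.
- **Accelerometer.** Table 1 (section 7.2) places it on the thigh and lists its output as a daily physical activity score.

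Section 6.2.1 has physiotherapists supervising the sessions live over an app and webcam. No attendance register, platform log or call log is named as a source anywhere.

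Two adherence criteria appear in section 7.1. One asks that at least 70% of included participants complete at least 70% of planned sessions. The other, at the end of the section, makes a larger trial conditional on at least 52% of the intervention group receiving more than 60% of the intended interventions.

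**The concern.** The outcome is a count of sessions, but the named instruments measure other things. If the logbook is the booklet diary, it leaves out by definition the sessions to be counted. A thigh sensor registers leg movement. The programme is built "with 50/50% exercises for upper and lower extremities, respectively", and intervention patients are also told to walk briskly and do sit-stand exercises every day, so a burst of movement cannot be assigned to a tele-session. That leaves the patient's own account.

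Self-reported attendance is open to over-reporting, which pushes the figure upwards. The three numerator terms add to the problem, because a session that staff delivered is not necessarily one that the patient attended or finished. The figure feeds both adherence criteria, so an inflated count bears on whether the larger trial is judged feasible.

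**Working it through.** The protocol states no figure to reproduce here. The check is how many wrongly credited sessions it takes to change a result.

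**Inputs.** 3 tele-sessions and 1 call per week (end of section 6.2.5); minimum wait 2 weeks (section 4.1); 25 patients per arm (section 3.6); the two criteria in section 7.1.

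**Planned contacts.** Two weeks: 3 × 2 = 6 tele-sessions plus 2 calls = 8. Four weeks: 3 × 4 = 12 tele-sessions plus 4 calls = 16.

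**Arm-level thresholds.** 0.70 × 25 = 17.5, so 18 patients; 0.52 × 25 = 13 patients.

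**One credited session, two-week wait.**
- More than 60% of all contacts: 0.60 × 8 = 4.8, so 5 are needed. 4/8 = 50% fails; 5/8 = 62.5% passes.
- At least 70% of tele-sessions only: 0.70 × 6 = 4.2, so 5 are needed. 4/6 = 67% fails; 5/6 = 83% passes.

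**Arm-level illustration.** These are assumptions, not protocol figures: true attendance p per session, sessions independent, and a fraction f of missed sessions reported as attended. The reported rate is q = p + (1 − p)f. The chance that a patient is classed adherent is the binomial upper tail P(X ≥ r | n, q), where n is the number of tele-sessions and r the number needed. The chance that the arm meets its threshold is the upper tail of that probability over 25 patients.

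70%/70% criterion, tele-sessions only, p = 0.70:

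| f | q | Patient ≥9/12 (4 weeks) | Arm ≥18/25 (4 weeks) | Patient ≥5/6 (2 weeks) | Arm ≥18/25 (2 weeks) |
|---|---|---|---|---|---|
| 0 | 0.70 | 0.493 | 0.018 | 0.420 | 0.002 |
| 0.1 | 0.73 | 0.586 | 0.123 | 0.487 | 0.016 |
| 0.2 | 0.76 | 0.680 | 0.423 | 0.558 | 0.074 |
| 0.3 | 0.79 | 0.767 | 0.792 | 0.631 | 0.240 |

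With p = 0.60 and four weeks, the arm-level chance stays low: 0.000, 0.000, 0.003 and 0.070.

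52%/60% rule, tele-sessions only, four weeks (0.60 × 12 = 7.2, so at least 8 of 12):
- p = 0.70: the patient-level chance without over-report is 0.724 and the arm-level chance of at least 13 of 25 is already 0.991, so over-report hardly matters.
- p = 0.60: the patient-level chances for f = 0, 0.1, 0.2, 0.3 are 0.438, 0.554, 0.669 and 0.775; the arm-level chances are 0.265, 0.708, 0.961 and 0.999.

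Each criterion is therefore sensitive when true attendance lies near its own threshold, and not far from it.

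**The case against.** Several points on the other side stand.

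- **Calls are a source.** A reader might infer that no named source says anything about uptake. That goes too far. A weekly call can ask about attendance, and if it is the nurse call of section 6.2.5, a completed call evidences that counselling contact and an unanswered one is itself an observable non-event. The gap concerns tele-session attendance.
- **Logbook and diary.** The protocol never says that they are the same document. It is the likely reading, since no other patient activity record is described, but it is an inference.
- **Self-report suits part of the programme.** The exercise target covers the prescribed programme, which includes daily unsupervised tasks. A diary and a sensor are reasonable for those.
- **Loss of non-adherent patients.** A reader might infer that patients who return no booklet fall out of the denominator and so raise the rate. The document does not support this: section 7.1 sets the arm-level denominators as included participants and the intervention group, and handling of missing records can be left to an analysis plan that is not shown.
- **The 70% example does not carry over.** A patient at 4/6 = 67% already exceeds 60%. If both calls are counted as well, (4 + 2)/8 = 75% clears 70% without any over-report. That example holds only on an exercise-only reading.
- **Detail may come later.** Section 6.2.5 promises detailed protocols for sessions and calls, and section 11.1 provides worksheets and an eCRF. A register could sit there. Section 7.1 nevertheless already names its sources, and these do not include one, so later documents would have to depart from it.

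**Conclusion.** The point holds as a mismatch between a defined outcome and its stated sources. For tele-exercise sessions, the larger part of the planned contacts (6 of 8 in two weeks), section 7.1 relies in effect on self-report when direct observation is available.

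The size depends on true attendance and the over-report rate, neither of which the protocol gives. At patient level, one credited session is enough to cross a line on a two-week wait. At arm level, under the assumptions above, four weeks at 70% true attendance with a fifth of missed sessions misreported raises the chance of meeting the 70%/70% criterion from 0.018 to 0.423. The 52%/60% rule is exposed in the same way near 60% attendance, but barely at 70%.

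The documents do not show that over-reporting will occur, nor that the progression decision will be wrong. They show that the stated method could not detect it. The correction is worth making before recruitment because attendance not recorded at the time is hard to recover.

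**What to change.** In section 7.1:

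1. Take the numerator from a per-session attendance record kept by the supervising physiotherapist (or the platform log), and from a nurse call log for counselling.
2. Use one term, sessions attended, in place of *delivered*, *applied* and *completing*.
3. Keep the wait-based denominator for each patient, and state that all patients randomised to the intervention are counted.
4. Record sessions that the site did not offer separately, so that they are not read as patient non-adherence.
5. Report diary and accelerometer data as a separate measure of unsupervised home activity.
6. Reconcile section 6.2.1 with section 7.1: say whether the booklet diary and the logbook are one document and what it covers, and whether the weekly calls are the nurse counselling calls.

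The cost is a tick-list per contact, kept by staff who are already present and who, under the safety paragraph of section 7.1, already note undesirable effects at these contacts. Measured adherence may come out somewhat lower than self-report.

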2.1 Primary objective

The primary objective of this feasibility study is to determine if it is feasible for patients awaiting elective CABG surgery to participate in a preoperative homebased multimodal prehabilitation intervention. We will evaluate this through completion of the following objectives:

- Assess the proportion of eligible patients that are recruited into the study.
- Assess the suitability of inclusion and exclusion criteria by examining recruitment data.
- Explore reasons for non-consent to study participation.
- Assess the acceptability of the study to patients by measuring recruitment and retention to the study and thorough qualitative interview responses.
- Assess the acceptability of the intervention through qualitative interviews and retention rates during the study.
- Assess adherence to and completion of the intervention (i.e. do participants adhere and work through all components of the intervention) and explore engagement and satisfaction with the interventions by qualitative interviews.
- Assess the proportion of patients lost to follow-up after study entry.
- Assess safety of the interventions.
- Explore the appropriateness of outcome measures, completion rates and assess response to questionnaires through qualitative interviews.
- Evaluate the logistics of delivering a home-based tele-exercise training intervention through qualitative interview responses from both health care professionals and patients.
- Determine the “prehabilitation window” (length of time between MDT-conference and CABG surgery)

2.2 Secondary objective:

The secondary objectives will evaluate if the multimodal prehabilitation intervention has an impact on preoperative and postoperative outcomes. For this we will collect data on study outcomes to assess levels, variation, and changes over time, which can inform sample size for the future RCT, as shown in **Table 1**, section 7.2.

3. Method

[figure not shown]

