3.6 Sample size and power

As the primary aim of this study is to evaluate feasibility, there is no formal requirement for a formal power calculation.⁶² Sample sizes between 24 and 50 have been recommended.^{63,64} A sample size of 25 patients in each group was chosen as it seems reasonable to provide outcome data in a small sample, and at the same time a sample size large enough to investigate the additional aspects that are being assessed for feasibility⁶⁵ informing a future power calculation for a full-scale RCT.

4. Selection and allocation of participants

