Safety: Safety of the intervention will be determined based on the number and nature of adverse events (AE), which is defined as any discomfort or symptoms of angina pectoris that will prevent a patient to take part in the physical tele exercise sessions or symptoms that require medical attention. Adverse event (AE), serious AE (SAE), serious adverse reaction (SAR), and suspected unexpected serious adverse reaction (SUSAR) will be monitored during the trial counting the number of occurrences. In addition to the physiotherapist

taking note of any undesirable effect during and after the tele session or phone counselling with the project nurse, all participants are asked to report any symptoms that was not consistent with their usual physical condition presentation as a result of exercise sessions.

For a lager RCT trial to be deemed feasible, feasibility outcomes need to be attained, meaning that more than 60% of eligible patients will participate and at least 52% of the intervention group will receive more than 60% of the intended interventions.⁸⁷

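### Section 7.1 sets three unreconciled uptake thresholds for one feasibility question: 60% or more, at least 30%, and more than 60% of eligible patients

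*Protocol*

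**What the plan says.** The first objective listed in Protocol section 2.1 is: "Assess the proportion of eligible patients that are recruited into the study". Section 7.1 then sets criteria for that proportion in three places.

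- **Recruitment and retention rates:** "A proportion of 60% or more of patients awaiting elective CABG surgery who are eligible for the study is acceptable".
- **Adherence rates:** "Inclusion in the CABGpreHAB study must be attractive to at least 30% of eligible patients who meets the inclusion criteria".
- **Closing rule of 7.1, on when a larger RCT counts as feasible:** "more than 60% of eligible patients will participate and at least 52% of the intervention group will receive more than 60% of the intended interventions".

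The recruitment paragraph also defines the rate itself: "The recruitment rate will be determined by the number of individuals who participate in the study out of those who are eligible/admissible but refused to" take part.

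On size, section 3.6 states that "A sample size of 25 patients in each group was chosen as it seems reasonable to provide outcome data in a small sample", 50 in all, and that "there is no formal requirement for a formal power calculation". Section 9.1 limits the feasibility analysis to descriptive statistics.

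**The concern.** All three criteria concern the same event (entering the study) in the same population (eligible patients), yet one bar is half the height of the other two. None is labelled as a floor, a target or a tier, and no action is given for a result that falls between them.

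The study exists to inform a full-scale RCT. With no power calculation and a descriptive analysis, these thresholds are the only uptake test that the protocol fixes in advance. If they disagree, the bar can be chosen after uptake is known. The safeguards in section 3.4 (blinded analysis, conclusions drafted in two versions) do not prevent this, because uptake is not an arm-specific result.

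**Working it through.** The protocol derives no figure from these thresholds, so there is none to reproduce. The check compares the criteria directly and then translates them into numbers of patients.

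**1. Inputs.** Criteria from section 7.1: A, uptake ≥ 60% (recruitment paragraph); B, uptake ≥ 30% (adherence paragraph); C, uptake > 60% (closing rule). Planned enrolment from section 3.6: 25 × 2 = 50. Two assumptions: exactly 50 are enrolled, and uptake = participants ÷ all eligible patients. Objective 2.1 and the wording of all three criteria support that denominator.

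**2. Eligible patients at each bar.** Eligible = 50 ÷ uptake, so 50/0.60 = 83.3 and 50/0.30 = 166.7.

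| Eligible patients | Uptake | A (≥ 60%) | B (≥ 30%) | C (> 60%) |
|---|---|---|---|---|
| 83 | 50/83 = 60.2% | met | met | met |
| 84 | 50/84 = 59.5% | failed | met | failed |
| 100 | 50/100 = 50.0% | failed | met | failed |
| 166 | 50/166 = 30.1% | failed | met | failed |
| 167 | 50/167 = 29.9% | failed | failed | failed |

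From 84 to 166 eligible patients, B is met while A and C fail. With 83 or fewer all three are met; with 167 or more all three fail.

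**3. Can sampling variation blur the split?** For illustration, assume 100 eligible patients who decide independently (my assumption). The binomial probabilities of meeting each criterion are:

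| True uptake | P(meets B) | P(meets A) | P(meets C) |
|---|---|---|---|
| 45% | 0.999 | 0.002 | 0.001 |
| 55% | > 0.999 | 0.183 | 0.134 |

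At 45%, the answer depends almost wholly on which bar is applied.

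**4. Does the denominator matter?** Read literally, the definition in the recruitment paragraph is participants ÷ refusers. If eligible patients are participants plus refusers, a ratio of 0.60 is a share of 0.60/1.60 = 37.5% of eligible patients, and a ratio of 0.30 is 0.30/1.30 = 23.1%. The band in step 2 therefore depends on the denominator. The literal definition also disagrees with objective 2.1 and with the wording of the thresholds.

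**5. Exactly 60%.** A accepts it and C does not. With 50 enrolled it cannot occur, since 83.3 is not a whole number. This is a matter of tidying the wording and adds no weight.

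**The case against.** The strongest reply is that only the closing sentence of 7.1 says when a larger RCT is feasible, and it requires more than 60%. The 30% sentence is worded as a minimum and nowhere says that 30% is enough. Read this way, 45% uptake clears a minimum, fails the RCT rule, and the answer is not feasible. A reader might infer that an uptake between the bars is equally a success and a failure. The documents do not support that: no sentence licenses a finding of feasibility at 30%.

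This part of the reply stands, but it does not remove the problem. Beside a mandatory bar above 60%, a mandatory 30% floor does no work, so it is either redundant or meant for something the text does not state. Reading it as interest rather than enrolment does not help: its subject is inclusion in the study, no separate measure of interest is defined, and interest could not be lower than enrolment. The closing rule also refers in general to the feasibility outcomes being attained, which could be read as pointing back to the earlier criteria, the 30% among them.

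It is also fair to say that observed uptake will be reported whichever bar applies, and that neither participant safety nor an inferential error rate is at stake. That limits the harm to the progression decision. That decision is the study's purpose.

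**Conclusion.** The inconsistency is real and in the current text: three thresholds for one quantity, with no ranking. An uptake of at least 30% but below 60% meets one stated criterion and fails the other two. Given 50 enrolled and all eligible patients as denominator, this is 84 to 166 eligible patients, or 59.5% down to 30.1%. If enrolment differs from 50 or refusers alone are the denominator, the counts move; the conflict between the criteria does not.

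A reader might also infer that uptake is likely to fall in this band. The protocol gives no prior uptake figure, so nothing can be said about how likely that is. Nor do the documents show which threshold the sponsor intends. Because the point touches a primary feasibility criterion and can be cured by wording, it should be corrected.

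**What to change.** Before recruitment data are reviewed, amend section 7.1 so that it holds one uptake criterion, with one boundary wording and participants divided by all eligible patients as the stated rate. There are two ways to do this:

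- **Single bar.** For example, keep the closing rule's more than 60%, use the same wording in the recruitment paragraph, and delete the 30% sentence from the adherence paragraph.
- **Bands.** If 30% is meant as a lower bound, state explicit stop/amend/go bands. The action for 30–60% is for the sponsor to choose; the protocol gives none.

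In either case, correct the definition of the recruitment rate, whose literal denominator is refusers only.

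The closing sentence should be reconciled on adherence in the same edit. It asks for at least 52% of the intervention group to receive more than 60% of the interventions, while the adherence paragraph asks for at least 70% to complete 70% or more of sessions. Settling uptake alone would leave the progression rule inconsistent.

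The cost is protocol wording, with no change to sample size or data collection. The small downside is that the sponsor can no longer choose the bar once uptake is known.

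### Section 7.1 sets two unranked adherence criteria; on a common count, 13 to 17 adherent patients of 25 meets one and fails the other

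*Protocol*

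**What the plan says.** All the statements below define or feed the primary outcome in Protocol section 7.1, except where another section is named.

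- **Adherence rates paragraph, group criterion.** The interventions "must be widely accepted, with at least 70% of included participants completing 70% or more of the planned sessions", counted in the intervention group.
- **Closing paragraph, rule for the larger trial.** It opens "For a lager RCT trial to be deemed feasible, feasibility outcomes need to be attained" and spells this out as two conditions: "more than 60% of eligible patients will participate", and "at least 52% of the intervention group will receive more than 60% of the intended interventions".
- **Adherence rates paragraph, a third target.** Adherence is also judged against "individuals achieving > 70% of the prescribed exercise program (self-reported"; no share of participants who must reach it is given.
- **What is counted.** The same paragraph measures adherence as the "number of telephone counselling and tele-exercise sessions delivered out of the theoretical number that could have been delivered" over each patient's wait. The closing paragraph speaks of intended interventions and does not say whether these are the same sessions.
- **Section 6.2.1.** Outside the sessions, "Participants in the intervention will be instructed to perform daily exercise tasks such as brisk walking and sit-stand exercises", so the prescribed exercise program may be a different count from the sessions.
- **Section 9.1.** Adherence is to be reported as a percentage; no criterion is named there.

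**The concern.** The two group criteria differ both in the cut applied to each patient (70% or more against more than 60%) and in the share of patients who must pass it (70% against 52%). Only the closing paragraph names the decision on the larger trial, but the other criterion is worded as an obligation, and nothing makes one a target and the other a minimum.

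The order cannot safely be inferred from the rest of 7.1. If the Adherence rates paragraph held ambitions and the closing paragraph held minimums, the recruitment figures should follow the same pattern. One of them does not: "Inclusion in the CABGpreHAB study must be attractive to at least 30% of eligible patients who meets the inclusion criteria" is the lower recruitment figure, and the closing paragraph's figure is the higher one.

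Adherence is one of only two conditions set for calling the larger trial feasible. If adherence turns out moderate, the same data support both a positive and a negative verdict. Which sentence governs could then be settled once the result is known.

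**Working it through.** There is no protocol calculation to reproduce: section 3.6 makes no power calculation, and 7.1 gives the criteria only as percentages.

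**Inputs**
- Intervention group: 25 patients (section 3.6, allocation 1:1).
- Criteria: 70% of patients at 70% or more; 52% of patients above 60% (section 7.1).
- Contacts: three web sessions and one call per week, so 4 per week (end of section 6.2.5).
- Waits: 2 weeks is the minimum in section 4.1; 4 weeks is the upper end of the range in section 1.2.2.
- Assumption: intended interventions means the planned sessions.

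**Step 1. Patients needed.** 0.70 × 25 = 17.5, so 18 patients. 0.52 × 25 = 13 patients.

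**Step 2. One common cut per patient.** Let X be the number of adherent patients. If X is 13 to 17, the closing rule is met (X ≥ 13) and the other fails (X < 18). The reverse cannot occur, because 18 or more is also 13 or more. With fewer analysed patients the zone shifts but remains: 13 to 16 of 24, and 11 to 13 of 20.

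If patients adhere independently with true share p, X is Binomial(25, p), and the chance of conflict is P(X ≥ 13) − P(X ≥ 18):

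| Assumed p | P(X ≥ 13) | P(X ≥ 18) | Conflict |
|---|---|---|---|
| 0.55 | 0.694 | 0.064 | 0.630 |
| 0.60 | 0.846 | 0.154 | 0.693 |
| 0.65 | 0.940 | 0.306 | 0.633 |
| 0.70 | 0.983 | 0.512 | 0.471 |
| 0.75 | 0.997 | 0.727 | 0.270 |
| 0.80 | 1.000 | 0.891 | 0.109 |
| 0.85 | 1.000 | 0.975 | 0.0255 |

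**Step 3. Each criterion at its own cut.**
- Over 2 weeks (8 contacts): 0.70 × 8 = 5.6, so 6 contacts; more than 0.60 × 8 = 4.8, so 5 contacts.
- Over 4 weeks (16 contacts): 0.70 × 16 = 11.2, so 12 contacts; more than 0.60 × 16 = 9.6, so 10 contacts.

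The conflict zone is now wider. If all 25 patients attended 5 of 8 contacts (62.5%), the closing rule would be met by 25 of 25 and the other criterion by none.

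Let X60 and X70 be the numbers of patients reaching each cut, with contacts per patient taken as beta-binomial. Eighteen patients at the higher cut implies at least 13 at the lower, so the chance of opposite verdicts is P(X60 ≥ 13) − P(X70 ≥ 18). Mean attendance and the within-patient correlation are assumed:

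| Mean attendance | Correlation 0.1 (2 wk / 4 wk) | Correlation 0.3 (2 wk / 4 wk) | Correlation 0.5 (2 wk / 4 wk) |
|---|---|---|---|
| 70% | 0.913 / 0.971 | 0.850 / 0.900 | 0.768 / 0.812 |
| 80% | 0.248 / 0.356 | 0.318 / 0.417 | 0.284 / 0.346 |
| 85% | 0.033 / 0.047 | 0.084 / 0.123 | 0.083 / 0.110 |
| 90% | 0.001 / 0.001 | 0.007 / 0.012 | 0.009 / 0.013 |

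The two tables use different scales: the share of patients who are adherent in Step 2, and mean attendance per patient in Step 3.

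**Step 4. Precision.** Exact (Clopper-Pearson) 95% intervals are 31.3% to 72.2% for 13 of 25 and 50.6% to 87.9% for 18 of 25. They overlap widely.

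**The case against.** The best defence is that the two criteria do different jobs. Only the closing paragraph is written as a decision rule. The 70%/70% sentence speaks of acceptance and is followed by interviews about withdrawals, and section 2.1 lists acceptability and adherence as separate objectives. On that reading 52%/60% decides progression and 70%/70% is an acceptability target. The reading is possible, but the protocol does not state it. The 70%/70% sentence stands under Adherence rates, is worded as an obligation, and belongs to the feasibility outcomes that the closing paragraph says need to be attained.

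Three further points have some force.

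- **Recruitment comparison.** It is only partial support. Section 7.1 also calls 60% or more acceptable for recruitment, which nearly matches the closing paragraph; only the 30% sentence runs the other way.
- **What is counted.** If intended interventions include the nutrition, smoking or alcohol components, the 13-to-17 zone and the probabilities no longer apply. The defect is then an undefined term in a primary decision rule, which still needs correcting.
- **Size of the stake.** This is a descriptive pilot, adherence will be reported as a percentage, and 25 patients cannot separate 52% from 70%. That limits how much weight either threshold can bear. It does not justify leaving open which one applies.

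A separate analysis plan would not cure this. Choosing one criterion there would still leave the other standing in the protocol.

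**Conclusion.** The concern holds. Section 7.1 fixes two different adherence thresholds for the primary feasibility outcome, does not rank them, and leaves the quantity in one of them undefined.

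The firm result is 18 against 13 of 25 patients, with opposite verdicts at 13 to 17. It rests on 25 intervention patients, a common session count and one cut per patient. The probabilities also depend on assumed adherence, for which the protocol gives no value. With each criterion at its own cut, and over correlations 0.1 to 0.5, opposite verdicts have a chance of 77% to 97% at 70% mean attendance, 25% to 42% at 80%, 3% to 12% at 85%, and 0.1% to 1.3% at 90%. The ambiguity is therefore serious if adherence is moderate and matters little if it is high. Because the criterion decides a primary outcome, it should be corrected before any adherence data are seen.

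**What to change.** Before randomisation, rewrite the adherence text in 7.1 in one of two ways:

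- state a single progression rule, with one cut per patient, one share of patients, one numerator, and all patients randomised to the intervention as denominator; or
- keep both figures and say explicitly which is the target and which is the minimum for progression.

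In either case, define the intended interventions and say where the target of more than 70% of the prescribed exercise program fits.

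Optionally, show tele-exercise and telephone adherence separately beside the combined figure: a patient who attends every exercise session and takes no calls scores 3/4 = 75%, above both cuts.

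The cost is a wording change in 7.1, with no new data, staff or visits. The rule would remain a decision on the point estimate, since the sample is too small to distinguish the two thresholds statistically.
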